3.5.3.2 Safety Variables

The safety variables to be measured after dosing include, but are not limited to, the variables as given below. A complete list of safety variables will be provided in the SAP.

- Adverse events
- Clinical laboratory (clinical chemistry, hematology, and urinalysis)
- Vital signs (supine blood pressure and pulse, respiratory rate, and body temperature)
- 12-lead ECGs

3.5.4 Drug Concentration Measurements

Total Radioactivity

The analysis of total radioactivity in whole blood, plasma, urine, and fecal (and vomitus, if produced) samples will be performed by TNO (Zeist, The Netherlands) under responsibility of ICON, using a validated AMS assay. The bioanalytical report(s) for these determinations will be included in the clinical study report (CSR).

The AMS isotope ratio will be converted to ng-eq/mL of whole blood, plasma, urine, or fecal homogenate (and vomitus, if applicable). The total radioactivity concentrations in urine and feces will be used to determine the percentage of dose recovered in urine and feces based upon the radioactive dose administered to each participant.

CCI [REDACTED]

GBT021601

The analysis of GBT021601 in whole blood, plasma, and urine samples will be performed at PPD Bioanalytical Laboratories (Middleton, US) under responsibility of the Sponsor, using a validated liquid chromatography with tandem mass spectrometry assay. The bioanalytical report(s) for these determinations will be included in the CSR.

CCI [REDACTED]

Metabolite Profiling and Identification

Metabolite identification including the structural identification of selected metabolites derived from [¹⁴C]-GBT021601 in whole blood and plasma samples, and selected, pooled urine and fecal samples will be performed by TNO (Zeist, The Netherlands) under responsibility of ICON, and in collaboration with the Sponsor. Pooling of biological samples will be conducted after initial results have been provided to Sponsor. Results will be reported separately from the CSR.

CCI [REDACTED]

3.5.5 Retention of Blood and Urine Samples

Clinical Laboratory Samples

Blood and urine samples remaining after clinical laboratory assessments have been performed can be used by ICON to develop and test methods. ICON will process these samples anonymously. These leftover samples will be stored for a maximum of 1 year after which the samples will be destroyed.

Pharmacokinetic Samples

After PK assessments have been performed, any remaining samples of whole blood, plasma, urine, and feces (and vomitus, as applicable) will be stored at the laboratories described in Section 3.5.4 for research related to this clinical study, future research into further development of GBT021601 and/or treatment methods, or future analyses of GBT021601, drug metabolism, and/or PK analyses. The samples will be stored for a maximum period of 3 years, after which the samples will be destroyed.

CCI
[REDACTED]
[REDACTED]
[REDACTED]
[REDACTED]

3.6 Statistical Procedures and Determination of Sample Size

3.6.1 Analysis Sets

3.6.1.1 Safety Set

All participants who have received 1 dose of GBT021601.

3.6.1.2 Pharmacokinetic Set

All participants who have received 1 dose of GBT021601 and provided at least 1 measurable postdose PK concentration of GBT021601 or total radioactivity in whole blood or plasma.

3.6.2 Statistical and Analytical Plan for Pharmacokinetic and Safety Evaluation

A SAP will be generated by the Biostatistics Department of ICON; the SAP will be finalized prior to database lock. Full details of the analyses to be performed will be included in the SAP.

Any deviation from the SAP will be reported in the section “Changes in Planned Analysis” in the CSR.

3.6.2.1 Pharmacokinetic Evaluation

The PK parameters and their statistical evaluation will be included in the CSR for this study. All concentration data will be summarized using descriptive statistics and will be listed and summarized in tabular and/or graphical form. Missing PK data will not be imputed and any anomalous concentration values may be excluded from analysis at the discretion of the pharmacokineticist after review of available documentation. Any such exclusion will be discussed with the Sponsor’s clinical pharmacologist and clearly described in the CSR. Additional details about data analysis will be provided in the SAP.

Individual whole blood and plasma PK parameters will be determined for both total radioactivity and GBT021601. Individual CCI and urine PK parameters will be determined for GBT021601. Individual urinary and fecal excretion of total radioactivity over time will be determined. The ratio of whole blood to plasma for total radioactivity and GBT021601, and the ratio of CCI to plasma for GBT021601 will also be calculated. CCI and ratio with total radioactivity in whole blood/plasma will also be determined.

Summary statistics of PK parameters (primary and secondary) will be presented including number of participants, arithmetic means, geometric means, standard deviations, coefficients of variation, medians, and ranges (minimum, maximum). No inferential statistical analyses are planned.

3.6.2.2 Evaluation of Safety and Tolerability

Demographics (age, sex, ethnicity, and race) and baseline characteristics (height, weight, and BMI) will be summarized. Medical history and previous concomitant medications will be provided in a data listing.

Safety and tolerability will be assessed through AEs, clinical laboratory, vital signs, ECGs, and physical examination findings, and any other parameter that is relevant for safety assessment. All safety data will be presented in listings, including any clinically significant abnormalities. Descriptive summaries will be provided for AEs, clinical laboratory tests, vital signs, and ECG data. Urinalysis results, concomitant medications, and physical examinations will be presented in listings only.

3.6.3 Determination of Sample Size

The sample size is not based on statistical considerations, but on a conventional number of participants that is considered sufficient to achieve the study objectives while accounting for potential dropout participants given the length of the study.

3.7 Data Quality Assurance

The study may be audited by the Quality Assurance Department at ICON to assess adherence to the clinical study protocol (CSP) and Quality System. During the conduct of the study, process-related audits may be performed. An audit certificate outlining any audits and other related activities performed may be provided in the appendices of the final CSR.

The clinical research site will be monitored by the study monitor to ensure correct performance of the study procedures and assure that the study is conducted according to the relevant regulatory requirements. The eCRF entries will be verified with the source documentation.

Regulatory authorities, the IEC, and/or the Sponsor's clinical quality assurance group may request access to all source documents, eCRFs, and other study documentation for on-site audit or inspection. Direct access to these documents must be guaranteed by the Investigator, who must provide support at all times for these activities.

Quality control principles will be applied throughout the performance of this study. Review procedures will be followed at ICON for all documents that are generated in relation with the study.

An explanation will be given for all missing, unused, and spurious data in the relevant sections of the CSR. Details on the handling of spurious and missing data will be included in the SAP.

4. ETHICS

4.1 Independent Ethics Committee

The submission package including the CSP and the ICFs will be submitted for review and approval by the IEC of the foundation “Beoordeling Ethisch Biomedisch Onderzoek” (English translation: “Assessment of Ethics of Biomedical Research”) (PPD [REDACTED] [REDACTED]) prior to the eligibility screening. The composition of the IEC is in accordance with the recommendations of the World Health Organization, the International Council for Harmonisation (ICH) E6(R2) Guideline for Good Clinical Practice (GCP) (European Medicines Agency [EMA]/Committee for Medicinal Products for Human Use [CHMP]/ICH/135/1995),¹⁰ and the EU Clinical Trial Directive (Directive 2001/20/EC)¹¹ (see below). The submission package will also be shared with the CA in the Netherlands for a statement of no objection.

ICON will keep the IEC informed about the progress of the study. All changes in research activities and all unanticipated problems involving risks to human participants will be immediately reported to the IEC. In accordance with Section 10, Subsection 1, of the Dutch law on Medical Research in Human Participants (WMO, revised Dec 2015),¹² ICON will inform the participants and the IEC if anything occurs on the basis of which it appears that the disadvantages of participation may be significantly greater than was foreseen in the research proposal, or if further recruitment of participants in the study has been put on hold for that reason, whichever occurs first. The study may be suspended pending further review by the IEC, except insofar as suspension would jeopardize the participants’ health. ICON will take care that all participants are kept informed.

No changes will be made in the study without IEC approval, except when required to eliminate apparent immediate hazards to human subjects.

Notification of the end of the study will be sent by ICON to the CA in The Netherlands and to the IEC within 90 days after completion of follow-up for the last participant. In case a study is temporarily halted, ICON will notify the IEC immediately, including the reason for this. In case a study is ended prematurely, ICON will notify the IEC and the CA in The Netherlands within 15 days, including the reasons for the premature termination. A summary of the results of the study will be sent by ICON to the CA and the IEC within 1 year after the end of the study.

4.2 Ethical Conduct of the Study

This study will be conducted in accordance with the ethical principles that have their origin in the World Medical Association (WMA) Declaration of Helsinki, adopted by the 18th WMA General Assembly, Helsinki, Finland, Jun 1964, and subsequent amendments.¹³

This study is also designed to comply with ICH E6(R2) Guideline for GCP (EMA/CHMP/ICH/135/1995),¹⁰ and the EU Clinical Trial Directive Directive 2001/20/EC¹¹, as incorporated into Dutch Law.¹²

Guidelines adopted by the ICH and other relevant international guidelines, recommendations, and requirements will be taken into account as comprehensively as possible, as long as they do not violate local law.

Whenever the term “Investigator” is noted in the CSP text, it may refer to either the Investigator at the site or an appropriately qualified, trained, and delegated individual of the investigational site.

4.3 Participant Information and Consent

All participants will be informed verbally and in writing regarding the objectives, procedures, and risks of study participation. The participants will have to sign the Dutch or English version of the ICF before any study-related procedures are started. The ICF contains information about the objectives of the study, the procedures followed during the study, and the risks and restrictions of the study, with special reference to possible side effects of the study drug and potential interactions. In addition, insurance coverage provided during the study is explained. The elements addressed in the ICF are according to the ICH E6(R2) Guideline for GCP (EMA/CHMP/ICH/135/1995).¹⁰

4.4 Privacy

All personal details will be treated as confidential by the Investigator and staff at ICON, the Sponsor, and any subcontractors involved, and handling of personal data will be in compliance with the EU General Data Protection Regulation.¹⁴

5. STUDY ADMINISTRATIVE STRUCTURE

5.1 Distribution of Activities

5.1.1 Preparation of Study Drug

The study drug will be prepared at the ICON Pharmacy (Groningen, The Netherlands).

5.1.2 Laboratory Assessments

The analysis of clinical laboratory samples will be performed at the ICON Clinical Laboratory (Groningen, The Netherlands).

The analysis of total radioactivity in whole blood, plasma, urine, and fecal (and vomitus, if produced) samples will be performed by TNO (Zeist, The Netherlands) as described in Section 3.5.4.

The analysis of GBT021601 in whole blood, plasma, and urine samples will be performed at PPD Bioanalytical Laboratories (Middleton, US) as described in Section 3.5.4.

Metabolite profiling and identification of [¹⁴C]-GBT021601 in whole blood and plasma samples, and selected, pooled urine and fecal samples will be performed by TNO (Zeist, The Netherlands) in collaboration with the Sponsor, as described in Section 3.5.4.

CCI

5.1.3 Electronic Case Report Design

The eCRF design will be performed with the computer program Medidata Rave® Electronic Data Capture (Medidata Solutions, New York, NY, US) by the Database Programming Department of ICON.

5.1.4 Data Management

Data management will be performed with the computer programs Medidata Rave® Electronic Data Capture (Medidata Solutions, New York, NY, US), SAS® (SAS Institute Inc, Cary, NC, US), and EXACT (Kinship EXACT™, Kinship Technologies, a technology subsidiary of ICON) by the Data Management Department of ICON.

5.1.5 Statistics

An SAP will be provided by the Biostatistics Department of ICON. The safety analysis and the statistical evaluation of PK parameters will be conducted by the Biostatistics Department of ICON. Statistical analysis will be performed with the computer program SAS® (SAS Institute Inc, Cary, NC, US). PK parameters will be calculated using Phoenix WinNonlin (Certara, Princeton, NJ, US). Additional PK computations can also be performed in SAS®.

5.1.6 Clinical Study Report Writing

The CSR, structured in accordance with the guideline “Structure and Content of Clinical Study Reports - ICH E3”,¹⁵ will be written by ICON.

5.2 Documentation**5.2.1 Archiving**

All documents concerning the study will be kept on file in the Central Archives of ICON for at least 25 years after conduct of the study. The Sponsor will receive the completed eCRFs (upon request, as PDF file).

5.2.2 Recording of Data in Source Documents and Electronic Case Report Forms

A data management plan will be written by the Data Management Department of ICON, which will be finalized prior to performing any data validation. The generated study data at the clinical research center will be collected on paper source documents. The clinical data manager will provide data entry access to the designated staff for data entry into the eCRFs. The clinical data manager will provide study-specific eCRF completion guidelines to the clinic personnel to facilitate data entry and to the clinical research associates to facilitate source data verification. Printouts of laboratory reports and ECG tracings are appendices to the source documents and are kept in the participant charts in addition to any other required ancillary source documents. Screen failures will not be entered into the database for this study.

6. CONFIDENTIALITY AND PUBLICATION POLICY

All information generated in this study is considered highly confidential and must not be disclosed to any person or entity not directly involved with the study unless prior written consent is gained from the Sponsor. However, authorized regulatory officials, the Sponsor and its authorized representatives are allowed full access to the records.

All study participants must be informed that their personal study-related data will be used by the Sponsor in accordance with local data protection law. The level of disclosure must also be explained to the participant, who will be required to give consent for their data to be used as described in the ICF. The participants must be informed that their medical records may be examined by auditors or other authorized personnel appointed by the Sponsor, by appropriate IEC members, and by inspectors from regulatory authorities.

Identification of participants and eCRFs shall be by unique participant numbers only.

All personal details will be treated as confidential by the Investigator and staff at ICON.

All relevant aspects regarding publication will be part of the contract (or similar document) between the Sponsor and ICON.

8. APPENDICES

8.1 Drug Accountability

The study drug will be kept in the ICON Pharmacy or in a locked and secured storage facility accessible to the pharmacist and the pharmacy assistant only.

The responsible pharmacist will keep an inventory. This will include a description of the formulation and the quantity of study drug received for the study and a record of what is dispensed, to whom, and when. Details of accountability oversight are in the Monitoring Plan.

On termination of the study, the responsible pharmacist will conduct a final inventory of the study drug supply and will record the results of this inventory in the Drug Accountability Form. Unused study drug will be locally destroyed according to the clinical site's SOPs.

8.2 Adverse Events and Serious Adverse Events Evaluation and Reporting

8.2.1 Adverse Events

An AE is any unfavorable and unintended sign (including an abnormal laboratory finding), symptom, or disease temporally associated with the use of a medical treatment or procedure that may or may not be considered related to the medical treatment or procedure. AE definitions will be followed as stated in the "Note for Guidance on Clinical Safety Data Management: Definitions and Standards for Expedited Reporting" (ICH topic E2A).¹⁶

All AEs reported by the participants or apparent from their physical appearance during the clinical study will be reported on the AE eCRF page.

Whenever possible, the severity of AEs will be graded using the most recent version of the CTCAE 5-point scale:

- **Mild (Grade 1):** Asymptomatic or mild symptoms; clinical or diagnostic observations only; intervention not indicated.
- **Moderate (Grade 2):** Minimal, local, or noninvasive intervention indicated; limiting age-appropriate instrumental activities of daily living.
- **Severe (Grade 3):** Severe or medically significant but not immediately life-threatening; hospitalization or prolongation of hospitalization indicated; disabling; limiting self-care activities of daily living.
- **Life-threatening (Grade 4):** Life-threatening consequences; urgent intervention indicated.
- **Death (Grade 5):** Death related to AE.

If an AE has multiple aspects, the aspect with the highest severity will be graded.

It is emphasized that the term “severe” is a measure of severity; thus, a severe AE is not necessarily serious. For example, itching for several days may be rated as severe, but may not be clinically serious.

In addition, clinically significant changes in physical examination findings and abnormal objective test findings (eg, laboratory, x-ray, ECG) should also be recorded as AEs. Test findings and physical examination findings can result in AEs if they:

- Are associated with accompanying symptoms, and/or
- Require additional diagnostic testing or medical/surgical intervention, and/or
- Lead to a change in study dosing or discontinuation from the study; result in the addition of significant additional concomitant drug treatment or other therapy, and/or
- Lead to any of the outcomes included in the definition of an SAE, and/or
- Are considered to be an AE by the Investigator or Sponsor.

Reporting as an AE should not be triggered by:

- Merely repeating an abnormal test, or
- Any abnormal test result that is determined to be an error.

The relationship of any AE to the study drug will be assessed and graded as related or not related:

Related:

- The AE follows a reasonable temporal sequence to study drug administration, and cannot be reasonably explained by the participant's clinical state or other factors (eg, disease under study, concurrent diseases, or concomitant medications).
- The AE follows a reasonable temporal sequence to study drug administration, and is a known reaction to the drug under study or a related chemical group, or is predicted by known pharmacology.

Not Related:

- The AE does not follow a reasonable sequence from study drug administration, or can be reasonably explained by the participant's clinical state or other factors (eg, disease under study, concurrent diseases, and concomitant medications). If an SAE is not considered to be related to study drug, then an alternative explanation should be provided.

8.2.2 Serious Adverse Events

An SAE is any untoward medical occurrence that, on the basis of medical and scientific judgment:

- Results in death, or
- Is life-threatening (this refers to an event in which the patient was at risk of death at the time of the event; it does not refer to an event which hypothetically might have caused death if it were more severe), or

- Requires inpatient hospitalization for a medical reason or prolongation of existing hospitalization (this refers to hospital admission required for treatment of the AE). (Note: this does not include confinement in, for example, a respite unit; a skilled nursing unit; rehabilitation facility; the clinical research center; or confinement due to planned or unplanned reason unrelated to study), or
- Results in persistent or significant disability/incapacity, or
- Is a congenital anomaly/birth defect.

Medical and scientific judgment should be exercised in deciding whether expedited reporting is appropriate in other situations, such as important medical events that may not be immediately life-threatening or result in death or hospitalization, but may jeopardize the patient or may require intervention to prevent one of the other outcomes listed in the definition above. These should also usually be considered serious. Examples of such events are intensive treatment in an emergency room or at home for allergic bronchospasm, blood dyscrasias, or convulsions that do not result in hospitalization.

SAEs will be collected from signing the ICF until the EoS/ET visit. SAEs that continue beyond the normal collection period (ie, are ongoing at the time a participant exits the study) will be followed until resolution or until stabilized with sequelae, or until reasonable attempts to determine resolution of the event are exhausted. SAEs that begin after the participant's participation in the study is complete, may be reported at any time.

The Investigator or clinical site personnel must notify the Sponsor or designee of all SAEs and any urgent safety matters, regardless of relationship to the investigational drug, within 24 hours of clinical site personnel becoming aware of the event. The Investigator will provide the initial notification by sending a completed "SAE Notification Form," which must include the Investigator's assessment of the relationship of the event to investigational drug and must be signed by the Investigator.

In addition, notification is sent by ICON to the IEC and the participant's General Practitioner.

Follow-up information, or new information regarding an ongoing SAE, must be provided promptly to the Sponsor or designee.

All SAE reports should be sent to the Sponsor or designee, as per the instructions provided to the site.

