14.3.1 Adverse Events		
Table 14.3.1.1	Overview of Treatment-Emergent Adverse Events	Safety
Table 14.3.1.2	Summary of Treatment Emergent Adverse Events by System Organ Class and Preferred Term	Safety
Table 14.3.1.3	Summary of Related TEAEs by System Organ Class and Preferred Term	Safety
Table 14.3.1.4	Summary of Treatment Emergent Adverse Events by Severity and Relatedness	Safety
14.3.2 Listing of Deaths and	Other Serious Adverse Events	
Table 14.3.2.1	Deaths	All Participants
Table 14.3.2.2	Serious Adverse Events	All Participants
14.3.3 Narratives of Adverse	Events Leading to Discontinuation From the Study	
Table 14.3.3	Not part of TFL – Reserved for Narratives in CSR	

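### Read literally, the hospitalization note in Protocol 8.2.2 takes an unplanned admission judged unrelated to the study out of the hospitalization criterion for an SAE

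*Protocol*

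**What the plan says.** Protocol 8.2.2 lists five outcomes that make an event serious. The third reads "Requires inpatient hospitalization for a medical reason or prolongation of existing hospitalization (this refers to hospital admission required for treatment of the AE"), with no condition on relatedness. A note in the same bullet then removes certain stays: respite, skilled nursing and rehabilitation facilities, the clinical research center, "or confinement due to planned or unplanned reason unrelated to study".

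Elsewhere the protocol keeps relationship separate:

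- Section 8.2.1 defines an AE as an event "temporally associated with the use of a medical treatment or procedure that may or may not be considered related to the medical treatment or procedure".
- Under the relatedness grading in 8.2.1 it adds: "If an SAE is not considered to be related to study drug, then an alternative explanation should be provided".
- Section 8.2.2 says the site "must notify the Sponsor or designee of all SAEs and any urgent safety matters, regardless of relationship to the investigational drug", and the notification form must carry the investigator's view of relationship.

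The SAP gives no definition of its own. Section 17.1.2 promises a listing of all SAEs, which is Table 14.3.2.2 in Appendix 3, titled "Serious Adverse Events".

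**The concern.** The last limb of the note is defined by the reason for the stay, not by the place. It covers unplanned as well as planned reasons, and its only qualifier is that the reason is unrelated to the study. An emergency admission for an intercurrent illness or injury fits those words as soon as the site takes it to be unrelated.

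The notification rule cannot repair this, because it applies only to events already classed as SAEs. An admission that the note has removed, and that meets no other criterion, never reaches it. At stake are the downstream steps that depend on SAE status, and consistency between the people classifying events, since one bullet gives two answers for the same admission.

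**Working it through.** No arithmetic decides this point. The check is to follow one case through the text: a participant has an AE after discharge from the unit, is admitted to hospital unplanned for treatment, and the investigator judges the cause unrelated to the study.

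1. **Is it an AE?** Yes. By 8.2.1 the event counts as one "that may or may not be considered related to the medical treatment or procedure".
2. **Does it meet the main clause of the hospitalization criterion?** Yes. It is an admission needed to treat the AE.
3. **Does the note remove it?** Literally, yes. The reason is unplanned and judged unrelated to the study. No passage in either document limits this limb to elective, social or other stays without an AE. Steps 2 and 3 therefore conflict within one bullet.
4. **Is there another route to seriousness?** Possibly. Death, threat to life, disability and congenital anomaly carry no such exclusion. Important medical events may also be classed as serious, by judgment. If one of these applies, the note does no harm.
5. **If none applies, what is lost?**
   - the 24-hour notice to the sponsor (8.2.2);
   - the notice to the ethics committee and the general practitioner (8.2.2);
   - entry to 8.2.3, where a SUSAR is by definition an SAE first;
   - a line in the SAE listing (SAP 17.1.2, Table 14.3.2.2).
6. **What is kept?** The event goes on the AE page of the eCRF with severity, relationship and outcome (Protocol 3.5.1.2.1 and 8.2.1). It also appears in the AE listing, which includes non-treatment-emergent events (SAP 17.1.1, Listing 16.2.7.1).
7. **Is the SAE count in Table 14.3.1.1 affected?** Only in part. SAP 17.1.1 restricts AE summaries to treatment-emergent events, which must occur before Study Day 56 or study discontinuation, whichever is earlier.

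The order of steps shows the same conflict. Under the notification rule, seriousness is settled first and relationship is then reported on the form. Under the note, relationship is settled first and helps to decide seriousness. The remark in 8.2.1 on explaining unrelated SAEs assumes the first order.

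The time window can be sized, though not the number of events. From discharge on Day 29 to the last visit on Day 206 is 206 − 29 = 177 days at most, including the 24-hour return stays. Of these, 56 − 29 = 27 days fall before the Day 56 cutoff. The remaining 177 − 27 = 150 days fall outside Table 14.3.1.1 however an event is classed. In that later period the loss can touch only the SAE listing and the notification steps.

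**The case against.** The best defence is that the limb was meant for stays not driven by an AE. The items before it are mostly non-acute settings, the noun is confinement rather than hospitalization, and the main clause already counts admission to treat an AE. The recognition of unrelated SAEs in 8.2.1 and the relationship-blind notification rule both favour that narrower intent. This reading is possible, and it is probably what was intended, but the note does not state it. The research center and care facilities are already named, so the last limb adds something further, and it says in terms that unplanned reasons are included.

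A second argument is that the note speaks of relation to the study, whereas the notification rule speaks of relation to the investigational drug. This narrows the conflict without removing it. A reason unrelated to the study is also unrelated to the study drug, so the note still removes some events for which the rule says relationship does not matter.

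A third argument is that the notification rule governs events already classed as SAEs, so the two sentences do not strictly contradict each other. That is correct. The conflict is between a definition and the evident intent of the section around it.

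Some stronger readings should be resisted:

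- A reader might infer that an unrelated emergency admission can never be an SAE. The note touches one criterion only.
- A reader might infer that such events vanish before the sponsor can see them. They remain recorded and listed as AEs, entries are verified against source (Protocol 3.7), and the sponsor has access to the records (Protocol 6).
- A reader might treat one participant in 8 to 10 as the size of the effect. That is only one divided by the sample size, for an event nobody has predicted.

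**Conclusion.** The point holds as a defect of wording with a practical consequence. On its literal reading, the note in 8.2.2 removes an unplanned admission for an AE from the hospitalization criterion when the admission is judged unrelated to the study. That conflicts with the main clause of the same bullet, with the AE definition and the provision for unrelated SAEs in 8.2.1, and with the rule to notify SAEs "regardless of relationship to the investigational drug, within 24 hours of clinical site personnel becoming aware of the event".

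The consequence is limited to misclassification and lost expedited notice for admissions that meet no other criterion. The SAE count in Table 14.3.1.1 can be wrong only for events before Day 56. The conclusion assumes that a site would apply the note as written. A site that read it narrowly would lose nothing, but the text does not tell it to. With no admission rate in the documents, no expected number of affected events can be given. In a study of 8 to 10 healthy participants it may well be none.

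**What to change.** Reconcile the note with the rest of Section 8.2. Delete *or unplanned*, and limit the exclusion to stays that are not for treatment of an AE, such as pre-planned admissions or stays in the research unit. Add a sentence that seriousness is judged independently of relationship to the study or the study drug. The SAP text needs no change, because its listing follows the protocol's SAE classification.

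The cost is a short change to one section, with the ethics committee approval that Protocol 4.1 requires for changes in the study, and possibly a few more SAE forms. No visits, samples or procedures are added.
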